6.1.1 Data Elements/Information

The presence of any pre-administration event (baseline signs and symptoms present just before radiation) will be recorded in the clinical research database:

- The date and time of evaluation
- The onset time
- The resolution time or duration
- Action taken
- Status of symptom
- Intensity
- Date of birth
- Demographic data
- Prior and concurrent medications
- Medical history and concurrent diseases
- Results of baseline tests: physical examination; vital signs; lab tests
- Questionnaire scores.

Personal data (including contact information) will be collected with the subject's permission and only to the extent that is necessary for the purposes of the study.

Exceptions to data collection:

- As androgen deprivation therapy (ADT) is given as part of standard of care, adverse events/toxicities that occur related to ADT will not be collected or reported.

The following data will be collected and evaluated according to the Study Calendar (Section 3.3):

- Physical examination
- Concomitant medications
- AEs
- Use of ADT
- Presence or absence of biochemical relapse
- Questionnaire scores

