3.1.1 Dose Limiting Toxicity

The DLT period includes treatment period (4, 3 or 2 weeks depending on Dose Level) and the 3 following weeks. DLT is defined as any of the following:

- Grade 3 rectal, small bowel, or urinary toxicity that does not resolve to Grade 2 or less within 4 days with appropriate medical management.
- Other grade 3 in-field toxicities attributable to RT that do not resolve to Grade 2 or less within 4 days with medical management.
- Delays of more than one week in completing radiation treatment due to toxicity (cumulative duration of delay over the course of the entire treatment).

Additionally, toxicities that occur more than 3 weeks after completion of treatment and during the 24 month follow up period will be followed and scored but will not be used for escalation with the following exception. If Grade ≥ 4 late bowel or bladder injury is observed in 2 patients at any Dose level, dose escalation will be terminated and the dose below that dose level in which the toxicity was observed will be considered the MTD. Early and late toxicities used for assessment of DLTs should be attributable (possible, probable or definite) to radiation. Changes in sexual and erectile function will not be considered a DLT. MTD will be determined for each Arm separately.

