4.1 ADT

We will allow patients to receive ADT on this trial after enrollment if deemed clinically appropriate, as the bulk of data suggests that it has no impact on the toxicities we have defined as DLTs in this trial.

ADT will be delivered on this protocol as per the current standard of care with the duration of therapy to be determined by the treating physician if indicated. This may include an anti-androgen, gonadotropin releasing hormone agonist, or the combination of both. As an alternative, patients may also receive ADT through their local care provider (medical oncologist, primary care physician, urologist) in collaboration with the research team.

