6 DATA COLLECTION AND EVALUATION

6.1 DATA COLLECTION

The PI will be responsible for overseeing entry of data into a 21 CFR Part 11-compliant data capture system provided by the NCI CCR and ensuring data accuracy, consistency and timeliness. The principal investigator, associate investigators/research nurses and/or a contracted

Abbreviated Title: Image guided radiation

Version Date: 06/03/2024

data manager will assist with the data management efforts. Primary and final analyzed data will have identifiers so that research data can be attributed to an individual human subject participant.

All adverse events, including clinically significant abnormal findings on laboratory evaluations, regardless of severity, will be followed until return to baseline or stabilization of event. Document AEs from the first study intervention through at least 30 days after the last study treatment administration. Beyond 30 days after the last study treatment administration, only adverse events which are serious and related to the study intervention need to be recorded.

An abnormal laboratory value will be considered an AE if the laboratory abnormality is characterized by any of the following:

- Results in discontinuation from the study (except for a rising serum PSA)
- Is associated with clinical signs or symptoms
- Requires treatment or any other therapeutic intervention
- Is associated with death or another serious adverse event, including hospitalization.
- Is judged by the Investigator to be of significant clinical impact
- If any abnormal laboratory result is considered clinically significant, the investigator will provide details about the action taken with respect to the test drug and about the patient's outcome.

End of study procedures: Data will be stored according to HHS, FDA regulations, and NIH Intramural Records Retention Schedule as applicable.

Loss or destruction of data: Should we become aware that a major breach in our plan to protect subject confidentiality and trial data has occurred, this will be reported expeditiously per requirements in section [7.2.1](#).

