8.4.3 Analysis of the Secondary Endpoint(s)

- Define the toxicity profile of image-guided, focally dose escalated prostate bed radiation in patients with a local or regional recurrence of prostate cancer after prostatectomy. All AEs except grade 1 with attribution to protocol treatment will be collected in tabulated way and analyzed.
- The rate of PSA control (biochemical progression free survival, bPFS) will be estimated by the Kaplan-Meier survival analysis and effects of clinical variables on bPFS will be assessed by the Cox proportional hazards model.
- The quality of life scores will be summarized at baseline and for each visit. Linear mixed effects model will be used to model quality of life scores at baseline and during and after treatment in which random intercept and random slope are used to account for patient-specific trajectory of quality of life scores. Changes of quality of life scores during and after treatment will be calculated from the estimated linear mixed effect model. The

similar analytical approach will be performed for depression scores and correlated with quality of life scores.

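### The collection exception for ADT-related events in 6.1.1 is not limited to events unrelated to radiation, so it conflicts with the rule that a possible relation to radiation is enough for a DLT

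*Combined protocol and SAP*

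**What the plan says.** The general collection rule is in section 6.1: "All adverse events, including clinically significant abnormal findings on laboratory evaluations, regardless of severity, will be followed". It adds "Document AEs from the first study intervention through at least 30 days after the last study treatment administration". After that point, only serious events related to the intervention need be recorded.

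Section 6.1.1 then lists an exception. Because ADT is given as standard of care, "adverse events/toxicities that occur related to ADT will not be collected or reported".

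For dose escalation, sections 3.1.1 and 8.4.4 use the same sentence: "Early and late toxicities used for assessment of DLTs should be attributable (possible, probable or definite) to radiation". For the toxicity profile, a secondary endpoint, section 8.4.3 says "All AEs except grade 1 with attribution to protocol treatment will be collected in tabulated way and analyzed". It does not say how strong the attribution must be. Section 8.4.4 has each event's relation to the study intervention recorded, and names no separate attribution to ADT.

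On ADT itself, section 4.1 says "We will allow patients to receive ADT on this trial after enrollment if deemed clinically appropriate", and gives the reason: "as the bulk of data suggests that it has no impact on the toxicities we have defined as DLTs in this trial". It also says "ADT will be delivered on this protocol as per the current standard of care". Section 1.2.1 supports that reason with two randomized trials in which adding ADT to salvage radiation did not raise bowel or bladder toxicity.

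**The concern.** The exception in 6.1.1 depends only on whether an event is related to ADT. The DLT rule depends only on whether it is at least possibly related to radiation. These are not opposites, and one event can satisfy both. For such an event one section requires that it count and another requires that it not be recorded.

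The exception also acts at collection, not at analysis. An event that was collected and then left out of a table can be brought back and re-attributed. One that was never entered is absent from the study data behind the escalation decision and the toxicity table. Attribution is made by investigators who know the treatment: assignment is direct and no blinding is described, although the text does not use the term open-label.

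At stake are the first secondary objective, safety and tolerability, and to a lesser degree the DLT count that defines the primary endpoint.

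**Working it through.** **1. The two rules side by side.** Each event can be classified by its two attributions.

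| Related to ADT | At least possibly related to radiation | 6.1.1 | 3.1.1 and 8.4.4 |
|---|---|---|---|
| No | Yes | Collected | Counts if it meets a DLT criterion |
| No | No | Collected | Does not count |
| Yes | No | Not collected | Does not count |
| Yes | Yes | Not collected | Counts if it meets a DLT criterion |

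Only the last row is in conflict, and no section states which rule prevails.

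**2. Can the last row occur?** Section 4.1 allows ADT after enrollment, and footnote 6 of the study calendar (3.3) provides for ADT started more than a month before radiation. Both treatments can therefore be active from the first fraction. Erectile change is an example from the protocol itself. Section 5.1.4 reports shrinkage of erectile tissue in men given radiation with ADT and suggests that ADT may explain much of it, while 9.3.2.1 lists declining erectile function as a radiation risk. The example applies chiefly to the period up to about 30 days after treatment, since 6.1 does not require later non-serious events to be recorded in any case.

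**3. Which uses of the data are exposed?**
- Toxicity profile (8.4.3): exposed for shared-attribution events above grade 1. I read protocol treatment there as radiation. Applying the possible threshold to the profile is an inference, because 8.4.3 states none.
- DLT count: erectile and sexual change is excluded by 3.1.1. Bowel and bladder events are covered by the trials cited in 1.2.1. That leaves mainly the criteria for other grade 3 in-field toxicity and for a toxicity delay of more than one week.

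**4. What one uncollected DLT does under 3.1.2.** The only design figure stated is the maximum sample size, which reproduces: 3 levels x 6 + 6 in expansion = 24 per arm, and 2 x 24 = 48. It is not in dispute. Under the decision table:
- 1 of 3 (add three patients) becomes 0 of 3 (escalate).
- 2 of 6 (stop) becomes 1 of 6 (the level passes).

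**5. Sensitivity, on assumed inputs only.** Let p be the true DLT rate and m the share of DLTs never collected, so that q = p(1 - m). With independent patients, the chance that a level passes is (1 - q)^3 + 3q(1 - q)^2 x (1 - q)^3.

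At p = 0.30 and m = 0: 0.343 + 0.441 x 0.343 = 0.494. At m = 0.10, q = 0.27: 0.389 + 0.432 x 0.389 = 0.557.

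| p | m = 0 | m = 0.10 | m = 0.25 | m = 0.50 |
|---|---|---|---|---|
| 0.20 | 0.709 | 0.752 | 0.814 | 0.906 |
| 0.30 | 0.494 | 0.557 | 0.654 | 0.814 |
| 0.40 | 0.309 | 0.378 | 0.494 | 0.709 |

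The documents give neither p nor m. The table shows the direction of the effect and how sensitive the rule is. It is not an estimate for this trial, and step 3 suggests that m is small.

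**The case against.** The strongest reply is that 6.1.1 is an exception to a general rule, and an exception is not a contradiction. Read with its stated reason, it most naturally covers events caused by ADT, leaving the specific DLT rule to govern anything possibly due to radiation. As between 6.1 and 6.1.1 this is right. It does not settle 6.1.1 against 3.1.1 and 8.4.4, because a rule about counting an event presupposes that the event was recorded, and 6.1.1 contains no such limit.

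Second, the protocol did consider ADT and concluded that it does not affect the DLT toxicities. This carries real weight for bowel and bladder events. The cited support does not cover other in-field toxicity or toxicity delays. It also comes from other regimens, and 1.2.2 describes this one as much more hypofractionated than those studied before in this setting.

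Third, attribution judgement is present in any unblinded phase I trial, and the fragility of 3+3 to one event is general. Both statements stand. Changing the wording would not remove the judgement: an event judged unrelated to radiation would still not count. It would ensure that shared events are recorded.

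Fourth, other information survives. ADT use, concomitant medications, examinations and questionnaires are collected, and 7.4.1 has the team discuss each patient at least every two weeks. It would therefore be too strong to say that no trace remains. However, the questionnaires are completed at baseline and every six months by English speakers only, and no planned analysis would bring such information back into the toxicity table.

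**Conclusion.** The point holds as a conflict between a collection rule and a counting rule. Taken literally, 6.1.1 removes events with shared attribution from the study data. The more likely effect is on the toxicity profile. An effect on the DLT count is possible but less probable, and the effect on the maximum tolerated dose is probably small. Its size cannot be estimated, because the documents give no share of men on ADT, no DLT rate and no rate of shared attribution. The conclusion rests on the literal reading of 6.1.1: an investigator may record shared events anyway, but the text does not require it. No numerical error in the plan is shown.

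Three stronger readings are tempting and are not supported:
- A reader might infer that men on ADT would show fewer recorded events than men not on ADT. This does not follow. Dropping events caused by ADT removes events that men not on ADT do not have. What follows is only that fewer events may be recorded than occurred.
- A reader might multiply an assumed share of men on ADT by an assumed share of ADT-attributed events to put a figure on the loss. Both inputs would be invented, and the product would include ADT-only events, which 8.4.3, as read above, would not tabulate.
- A reader might conclude that every ADT event should be collected. Leaving out ADT-only events is a deliberate choice for a standard-of-care treatment, and nothing here shows it to be wrong.

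**What to change.** In 6.1.1, restrict the exception to events judged related to ADT and unrelated to radiation. Add that any event at least possibly related to radiation is collected whatever its attribution to ADT, and is counted under 3.1.1, 8.4.3 and 8.4.4 where it otherwise meets their criteria. For those events, record the attribution to radiation and to ADT separately. The exclusion of sexual and erectile change from the DLT definition is untouched.

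The cost is a short text change, one attribution field on the case report form and a few more events to enter. No visit or procedure is added. If the protocol is right that ADT has no bearing on the DLT toxicities, the change will seldom affect a DLT count.

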6.2 DATA SHARING PLANS

6.2.1 Human Data Sharing Plan

What data will be shared?

I will share human data generated in this research for future research as follows:

- Coded and linked data in an NIH-funded or approved public repository.
- Coded and linked data in BTRIS (automatic for activities in the Clinical Center)

How and where will the data be shared?

- An NIH-funded or approved public repository: clinicaltrials.gov, dbGAP
- BTRIS (automatic for activities in the Clinical Center).
- Publication and/or public presentations.

When will the data be shared?

- At the time of publication or shortly thereafter.

6.2.2 Genomic Data Sharing Plan

Unlinked genomic data will be deposited in public genomic databases such as dbGaP in compliance with the NIH Genomic Data Sharing Policy

6.3 RESPONSE CRITERIA

For the purposes of this study, patients should be re-evaluated for response every 3 months after treatment with a serum PSA measurement as per the study calendar. Response will be assessed based on PSA.

6.3.1 Response Criteria

Biochemical control: Biochemical control will be defined as a post-radiation PSA that does not rise beyond 0.1 ng/dL.

Biochemical progression/biochemical failure: Serum PSA more than 0.1 ng/dL. At least 2 PSA measurements separated by 1 month are needed to confirm biochemical failure. If a PSA pre-

treatment was >0.1 ng/dL, a post-treatment value >0.1 ng/dL will not be considered biochemical progression if subsequent values continue to trend downwards after completion of radiation.

6.3.2 Biochemical Progression-Free Survival

Biochemical progression free survival (bPFS) will be evaluated on this trial as a secondary endpoint. bPFS is defined as the duration of time from start of treatment to time of PSA progression or death, whichever occurs first. PSA progression (also known as biochemical failure) is defined based on elevation of PSA beyond 0.1 ng/dL. A total of 2 rising PSA values separated by at least 1 month are required to document biochemical recurrence. If the PSA remains elevated, the date of failure will be backdated to the first PSA measurement that exceeded 0.1 ng/dL. Only PSA values collected at the NIH Clinical Center will be used to evaluate disease status given the variability in ranges obtained in different laboratories.

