3.7.2 Off-Study Criteria

- Completed study follow-up period
- Participant requests to be withdrawn from study
- Death
- Recurrence of prostate cancer
- PI discretion
- Non-compliance with follow-up visits or protocol mandated procedures
- PI decision to close the study
- Lost to follow up

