4 CONCOMITANT MEDICATIONS/MEASURES

Supportive care with blood components, antibiotics, analgesics, and general medical therapy will be provided if the need relates to the performance of protocol assessments (imaging procedures) or to treat side effects of therapy. Every effort will be made to refer the patient to their collaborating physician in the community for care unrelated to the protocol therapy or procedures. There are no limitations on the type of non-investigational concurrent medications allowed, as in general, these patients do not receive additional therapy for prostate cancer after radiotherapy, with the exception of hormonal therapy, which may be delivered as per the current standard of care.

Radiation related side effects will be managed as per the current standard of care without restrictions in medications or procedures that may be performed for management.

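### bPFS (Section 6.3.2) has no rule for new prostate cancer therapy, or off-study recurrence, before PSA failure is confirmed, so such patients can be carried event-free or informatively censored

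*Combined protocol and SAP*

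**What the plan says.** The endpoint is set in Section 6.3.2: "bPFS is defined as the duration of time from start of treatment to time of PSA progression or death, whichever occurs first". The same section adds "PSA progression (also known as biochemical failure) is defined based on elevation of PSA beyond 0.1 ng/dL", then "A total of 2 rising PSA values separated by at least 1 month are required to document biochemical recurrence", and on dating "If the PSA remains elevated, the date of failure will be backdated to the first PSA measurement that exceeded 0.1 ng/dL". It uses only NIH Clinical Center PSA values to judge disease status.

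Section 6.3.1 words confirmation a little differently: "At least 2 PSA measurements separated by 1 month are needed to confirm biochemical failure". For men whose PSA was above 0.1 ng/dL before treatment, it adds that "a post-treatment value >0.1 ng/dL will not be considered biochemical progression if subsequent values continue to trend downwards after completion of radiation".

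On therapy, Section 4 says these patients generally receive no further prostate cancer treatment after radiotherapy, "with the exception of hormonal therapy, which may be delivered as per the current standard of care". Section 4.1 allows ADT after enrollment, leaves its duration to the treating physician, and lets a local provider give it with the research team involved.

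Section 3.7.2 lists "Recurrence of prostate cancer" as an off-study criterion and does not say whether this means biochemical recurrence, clinical recurrence or either.

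Section 8.4.3 names Kaplan-Meier and Cox models for bPFS. It has no censoring rule for new therapy, clinical recurrence or leaving the study.

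**The concern.** Two kinds of patient can lose disease control without producing a bPFS event.

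The first starts new prostate cancer therapy because of a PSA rise or recurrence before a second NIH value has confirmed failure. If the therapy lowers the PSA, the confirmation rule is never met. Starting therapy is neither an event nor an off-study criterion, so he can be followed as event-free to month 24.

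The second is taken off study for recurrence without confirmed PSA failure. His follow-up stops because he failed. Kaplan-Meier and Cox analyses assume that a censored patient has the same later risk as those still followed, and here that assumption is doubtful.

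Measured against an endpoint that counts these patients, both routes push bPFS upward. That is the direction of the hypothesis in Section 8.1.2, which expects PSA control to look good beside published salvage series.

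**Working it through.** **Denominator.** Section 8.2 gives a maximum of 48. With two arms, three dose levels of up to six patients and an expansion of six per arm (Sections 3.1.2 and 8.2): 2 × (3 × 6 + 6) = 48, or 24 per arm. The figure reproduces. The plan states no bPFS target, power or event count to check.

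**One patient taken through the rule (PSA values assumed).** A man has a post-radiation NIH PSA of 0.2 ng/dL and starts new hormonal therapy. A month later:

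- Second value 0.3: two rising values above 0.1, so an event, backdated to the first. The rule works.
- Second value 0.05: not rising and no longer elevated. No event.
- Second value 0.15: still above 0.1 but not rising, so the two-rising-values condition of 6.3.2 is not met. If his pre-treatment PSA exceeded 0.1 and values keep falling, the downward-trend exception in 6.3.1 also applies. It does not exclude a fall caused by new therapy.
- No second NIH value: nothing that counts under 6.3.2. No event.

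**Size.** The documents give no rate of new therapy or of recurrence without PSA failure, so this is an illustration. Assume 24 patients and no other censoring. Assume six other confirmed PSA events, one each at months 3, 6, 9, 12, 15 and 18. Six of 24 leaves 75%, matching the approximate PSA control quoted in the Précis for standard treatment. One affected patient starts therapy or leaves just after month 6. The 2-year Kaplan-Meier estimate is:

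- Carried event-free: 18/24 = 75.0%.
- Counted as an event: 17/24 = 70.8%. The shift from carried is 1/24 = 4.2 points.
- Censored: two events by month 6 give 22/24. One of the 22 then leaves, so 21 remain and four later events leave 17/21. The estimate is 22/24 × 17/21 = 74.2%. The shift from censored to event is 74.2 − 70.8 = 3.4 points.

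Varying the assumptions, with one affected patient and differences taken from unrounded values:

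| Patients, other events, exit | Carried | Censored | Event | Carried − event | Censored − event |
|---|---|---|---|---|---|
| 24, 6, after month 6 | 75.0% | 74.2% | 70.8% | 4.2 | 3.4 |
| 24, 6, after month 12 | 75.0% | 74.6% | 70.8% | 4.2 | 3.7 |
| 24, 4, after month 6 | 83.3% | 82.9% | 79.2% | 4.2 | 3.8 |
| 24, 4, after month 12 | 83.3% | 83.3% | 79.2% | 4.2 | 4.2 |
| 48, 12, after month 6 | 75.0% | 74.6% | 72.9% | 2.1 | 1.7 |

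The four other events fall at months 3, 6, 9 and 12. The twelve fall two each at months 3, 6, 9 and 12 and one each at months 15, 18, 21 and 24.

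**The case against.** **Safeguards exist.** Footnote 7 of the Study Calendar says a second PSA will be obtained when failure is identified, and Section 4.1 involves the research team when ADT is given locally. Both narrow the first route. Neither closes it: footnote 7 prefers but does not require the NIH laboratory, 6.3.2 ignores outside values, and nothing covers therapy started before the second test.

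**A patient treated for lost control might be taken off study.** Recurrence or investigator discretion under 3.7.2 could remove him, so he would be censored and not carried. This is fair. It changes the size of the bias, but he is still not an event.

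**Recurrence in 3.7.2 may mean only biochemical recurrence.** On that reading, leaving the study coincides with the event and the second route closes. The term is undefined, so this cannot be ruled out.

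**Leaving out clinical recurrence is a design choice.** Sections 1.1.2 and 8.1.2 equate the endpoint with PSA control, and Section 6.3 assesses response on PSA. This largely stands, and it is why recurrence without PSA failure belongs in a sensitivity analysis. A reader might infer that the 6-month mpMRI regularly detects recurrences at PSA 0.1 ng/dL or below. The documents do not support that: the only purpose they state for a 6-month scan is exploratory measurement of erectile tissue (Sections 5.1.4 and 8.4.5).

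**The shift is small beside sampling error.** At 75% in 24 patients, a simple binomial 95% half-width is 1.96 × √(0.75 × 0.25/24) = 17.3 points. True, but this error runs in one direction and a rule removes it.

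**Conclusion.** The gap is real and confined to a secondary, descriptive endpoint. As written, a patient who starts new therapy for a PSA rise or recurrence before a confirming NIH value can be carried event-free. One who leaves for recurrence without confirmed PSA failure would be informatively censored. Each such patient in a full arm inflates 2-year bPFS by about 4.2 points if carried. If censored, the figure is about 3.4 points with exit at about 6 months and six other events, and 3.4 to 4.2 over the assumptions tried. The MTD is unaffected.

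Three stronger readings are not supported. A censored patient is not scored as controlled, so 4.2 points does not apply to everyone affected. The overall bias cannot be stated, because the documents do not show how often either route occurs. Nor can a biased comparison with the published series be claimed, because the documents do not say how those series defined failure.

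**What to change.** In Section 6.3.2:

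1. Count as a bPFS event the start of new prostate cancer therapy given for a PSA rise or documented recurrence. Date it to the first post-radiation PSA above 0.1 ng/dL in that rise if there is one, otherwise to the start of therapy.
2. State that ADT given as part of the initial treatment course, and its discretionary continuation without a PSA rise, is not an event. Section 4.1 leaves duration to the physician, so scoring every extension beyond a planned duration as failure would bias the rate downward.
3. In a sensitivity analysis, count removal from study for documented recurrence as an event, and say what documented recurrence means for that purpose.
4. Report the PSA-or-death version alongside.

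The cost is small. ADT use (Section 6.1.1), concomitant medications (Section 3.3) and, in remote follow-up, further tumor therapy (footnote 7) are already collected. The reason for starting therapy must be recorded as well. The reported bPFS may be slightly less favourable. No treatment or visit changes.
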